8.3.2 Method of Detecting Adverse Events and Serious Adverse Events

At each study visit, the participant will be queried on changes in his or her condition. During the reporting period, any unfavorable changes in the participant’s condition will be recorded as AEs, regardless if reported by the participant or observed by the Investigator.

Complete, accurate and consistent data on all AEs experienced for the duration of the reporting period (defined below) will be reported on an ongoing basis in the appropriate section of the eCRF. All SAEs must be additionally documented and reported using the appropriate Report Form as specified in [Appendix 4](#).

8.3.3 Follow-up of Adverse Events and Serious Adverse Events

Adverse events are recorded and assessed continuously throughout the study, as specified in Section [8.3.1](#) and are assessed for their outcome at the 28-day Safety Follow-up Visit.

All SAEs ongoing at the at the 28-day Safety Follow-up Visit must be monitored and followed up by the Investigator until stabilization or until the outcome is known, unless the participant is documented as “lost to follow-up”. Reasonable attempts to obtain this information must be made and documented. It is also the responsibility of the Investigator to ensure that any necessary additional therapeutic measures and follow-up procedures are performed. Further information on follow-up procedures is given in [Appendix 4](#).

Monitoring of Specific Adverse Events

If monitoring is warranted for certain treatment-related TEAEs for safety issues, the treating physician or Investigator is requested to follow the participant during the post-treatment Long-term Follow-up phase until the end of study period or the participant is “lost to follow-up” and report the management and outcome of AEs to the Sponsor.

8.3.4 Regulatory Reporting Requirements for Serious Adverse Events

The Sponsor will send appropriate safety notifications to Health Authorities in accordance with applicable laws and regulations.

The Investigator must comply with any applicable site-specific requirements related to the reporting of SAEs (particularly deaths) involving study participants to the Independent Ethics Committee/Independent Review Board (IEC/IRB) that approved the study.

In accordance with International Council for Harmonisation Good Clinical Practice, the Sponsor/designee will inform the Investigator of findings that could adversely affect the safety of participants, impact the conduct of the study, or alter the IEC's/IRB's approval/favorable opinion to continue the study. In line with respective regulations, the Sponsor/designee will inform the Investigator of AEs that are both serious and unexpected and considered to be related to the administered product ("suspected unexpected serious adverse reactions" or SUSARs). The Investigator should place copies of Safety Reports in the Investigator Site File. National regulations regarding Safety Report notifications to Investigators will be considered.

When specifically required by regulations and guidelines, the Sponsor/designee will provide appropriate Safety Reports directly to the concerned lead IEC/IRB and will maintain records of these notifications. When direct reporting is not clearly defined by national or site-specific regulations, the Investigator will be responsible for promptly notifying the concerned IEC/IRB of any Safety Reports provided by the Sponsor/designee and of filing copies of all related correspondence in the Investigator Site File.

For studies covered by the European Directive 2001/20/EC, the Sponsor's responsibilities regarding the reporting of SAEs/SUSARs/Safety Issues will be carried out in accordance with that Directive and with the related Detailed Guidance documents.

8.3.5 Pregnancy

Only pregnancies the Investigator considers to be related to the study intervention (e.g., resulting from a drug interaction with a contraceptive method) are AEs. However, all pregnancies with an estimated conception date during the period defined in Section 8.3.1 must be recorded in the AE page/section of the eCRF for both pregnancies in female participants and pregnancies in female partners of male participants. The Investigator must notify the Sponsor/designee in an expedited manner of any pregnancy using the Pregnancy Report Form, which must be transmitted by the same process specified for SAE reporting in [Appendix 4](#), section on Reporting Serious Adverse Events.

Investigators must actively follow-up, document and report on the outcome of all these pregnancies, even if the participants are withdrawn from the study.

The Investigator must notify the Sponsor/designee of these outcomes using the Pregnancy Report Form. If an abnormal outcome occurs, the SAE Report Form will be used if the participant sustains an event and the Parent-Child/Fetus AE Report Form if the child/fetus sustains an event. Any

abnormal outcome (e.g., spontaneous abortion, fetal death, stillbirth, congenital anomalies, ectopic pregnancy) must be reported in an expedited manner, as specified in Section 8.3.1, while normal outcomes must be reported within 45 days after delivery.

In the event of a pregnancy in a participant occurring during the study, the participant must be discontinued from study intervention. The Sponsor/designee must be notified without delay and the participant must be followed as indicated above.

8.4 Treatment of Overdose

For this study, any dose of bintrafusp alfa greater than 2 times (i.e., > 2400 mg) of the planned dose administered within a 24-hour time period will be considered an overdose.

Of note: In the dose-escalation study (EMR200647-001), participants safely received up to 30 mg/kg bintrafusp alfa every 2 weeks (including those with doses > 2400 mg) with no observed maximum tolerated dose (refer to the IB). Safety at significantly higher doses has not been clinically evaluated.

- In case of overdose with clinical correlation, symptomatic treatment must be used; there are no known antidotes for the compound.
- In the event of an overdose, the study intervention infusion should be discontinued, and participants should be observed closely for any signs of toxicity. Supportive treatment should be provided if clinically indicated.

Even if it not associated with an AE or a SAE, any overdose is recorded in the eCRF and reported to drug safety in an expedited manner. Overdoses are reported on a SAE Report Form, following the procedure in [Appendix 4](#), section on Reporting Serious Adverse Events.

If an AE occurs resulting from an overdose, it should follow SAE reporting criteria as indicated in [Appendix 4](#).

8.5 Pharmacokinetics

- Whole blood samples of approximately 3.5 mL will be collected for measurement of serum concentrations of bintrafusp alfa, as specified in the Schedule of Activities. The actual date and time (24-hour clock time) of each sample will be recorded to calculate actual time elapsed since the prior dose administration.
- The quantification of bintrafusp alfa in serum will be performed using a validated immunoassay method. Concentrations will be used to evaluate the PK of bintrafusp alfa.
- Remaining samples collected for analyses of bintrafusp alfa concentration may also be used to evaluate immunogenicity, safety or efficacy aspects related to concerns arising during or after the study.

Details on processes for collection and shipment of these samples are in the Laboratory Manual. Retention time and possible analyses of samples after the end of study are specified in the respective ICF.

Pharmacokinetic and antidrug antibody (ADA) samples will be collected according to [Table 2](#). Pharmacokinetic and ADA samples collected at the same time points may be used interchangeably if the dedicated sample has insufficient quantity as the participants will have consented to all collections and tests.

The PK parameters will be summarized using descriptive statistics (Table 7). Individual as well as mean concentration-time plots will be depicted.

The following PK parameters will be calculated, when appropriate:

Table 7 Pharmacokinetic Parameters

Symbol	Definition
C_{EOI}	The concentration observed immediately at the end of infusion
C_{trough}	The concentration observed immediately before next dosing (corresponding to predose or trough concentration for multiple dosing)

8.6 Pharmacodynamics

Not applicable.

8.7 Pharmacogenetics

- Where local regulations and IRB/IEC allow, a blood sample will be collected for DNA analysis from consenting participants. Participation in pharmacogenetic research is optional. Participants who do **not** wish to participate in the pharmacogenetic research may still participate in the study.
- In the event of DNA extraction failure, a replacement sample for pharmacogenetic testing may be requested from the participant. Additional informed consent will not be required to obtain a replacement sample.
- [Appendix 8](#) provides further information on pharmacogenetic research.

CCI

CCI

■

[figure not shown]
■

■

■

CCI

8.9 Immunogenicity Assessments

- Whole blood samples of approximately 5 mL will be collected for detection of antibodies against bintrafusp alfa in serum, as specified in the Bintrafusp alfa Pharmacokinetic, Immunogenicity Sampling (Table 2). Samples will be collected prior to any bintrafusp alfa administration on the same study day.
- The detection of antibodies to bintrafusp alfa will be performed using a validated assay method with tiered testing of screening, confirmatory and titration. Confirmed positive antibodies may be tested for the presence of neutralizing antibodies and may be further characterized.
- Remaining samples collected for analysis of anti-bintrafusp alfa antibodies may also be used to evaluate bintrafusp alfa concentration **CCI** during or after the study.
- Details on processes for collection and shipment of these samples are in the Laboratory Manual. Retention time and possible analyses of samples after the end of study are specified in the respective Main ICF.

CC

1

1

1

1

1

CCI

For more information, contact the Office of the Vice President for Research and Economic Development at [contact] or [contact].

For more information, contact the Office of the Vice President for Research and Economic Development at [contact] or [contact].

10. **What is the primary purpose of the *Journal of Clinical Endocrinology and Metabolism*?**

CCI

9.3 Populations for Analyses

The analysis populations are specified below. The final decision to exclude participants from any analysis population will be made by the team after careful consideration during a data review meeting prior to database lock.

For purposes of analysis, the analysis populations are defined in Table 10.

Table 10 Analysis Populations

Screening (SCR)	All participants, who provided informed consent, regardless of the participant's study intervention status in the study.
Safety (SAF)	All participants, who were administered at least 1 infusion of bintrafusp alfa.
Full analysis Set (FAS)	All participants, who were administered at least 1 infusion of bintrafusp alfa.
Pharmacokinetic (PK)	All participants who complete at least 1 infusion of bintrafusp alfa, and who provide at least 1 sample with a measurable concentration of bintrafusp alfa.
Immunogenicity	All participants who were administered at least 1 infusion of bintrafusp alfa and have at least one valid ADA result.

9.4 Statistical Analyses

Full details of all planned analyses will be described in the study Integrated Analysis Plan (IAP). Major modifications of planned analyses will be reflected in a protocol amendment or in the clinical study report (CSR).

In general, continuous variables will be summarized using number (n), mean, median, standard deviation, minimum, and maximum. Categorical variables will be summarized using frequency counts and percentages. Proportions are calculated based on the number of participants in the analysis set of interest, unless otherwise specified in the IAP.

9.4.1 Efficacy Analyses

Analysis of efficacy variables will also be performed on the Full Analysis Set (FAS) as well as subgroup of interest as listed in [Table 3](#), including but not restricted to PD-L1 expression.

Statistical analysis methods for primary and key secondary efficacy endpoints are summarized in Table 11. Further details will be specified in the IAP.

Table 11 Statistical Analysis Methods for Efficacy Analysis

Endpoint	Statistical Analysis Methods
Primary	
Confirmed objective response according to RECIST 1.1 assessed by an IRC	The ORR will be determined as the proportion of participants with a confirmed objective response of PR or CR. Confirmation of the response according to RECIST 1.1 will be required no sooner than 4 weeks after the initial documentation of CR or PR. The 95% CI for the ORR will be calculated using the Clopper-Pearson method.
Key Secondary	
DOR assessed by an IRC	DOR is defined as the time from first documentation of a confirmed objective response (CR or PR) according to RECIST1.1 to the date of first documentation of objective response of disease progression (PD) or death due to any cause whichever occurs first. The censoring rules for DOR are as described below for PFS. Kaplan-Meier estimates will be provided;

Endpoint	Statistical Analysis Methods
	Median DOR and the 95% CI for the median will be calculated according to Brookmeyer and Crowley (Brookmeyer 1982); Swimmer plots will be provided.
Durable response assessed by an IRC	A durable response is defined as an objective response (CR or PR) according to RECIST 1.1, determined by an IRC, with a duration of at least 6 months. Participants for whom the DOR is censored will be treated as failures (successes) in the analysis of durable response if the censored DOR is before (at least) 6 months. The DRR is defined as the percentage of participants with durable response. The 95% CI for the DRR will be calculated using the Clopper-Pearson method.
PFS according to RECIST 1.1 assessed by an IRC	PFS according to RECIST 1.1, is defined as the time from first administration of study intervention until date of the first documentation of PD or death due to any cause in the absence of documented PD, whichever occurs first. PFS data will be censored on the date of the last adequate tumor assessment for participants who do not have an event (PD or death), for participants who start new anticancer treatment prior to an event, or for participants with an event after 2 or more missing tumor assessments. Participants who do not have a baseline tumor assessment or who do not have any post-baseline tumor assessments will be censored on the date of first administration of study intervention unless death occurred on or before the time of the second planned tumor assessment, in which case the death will be considered an event. Kaplan-Meier estimates will be provided; Median PFS and the 95% CI for the median will be calculated according to Brookmeyer and Crowley (Brookmeyer 1982).
Overall survival	Overall survival is defined as the time from first administration of study intervention to the date of death due to any cause. Participants last known to be alive will be censored at date of last contact. Kaplan-Meier estimates will be provided; Median OS and the 95% CI for the median will be calculated according to Brookmeyer and Crowley (Brookmeyer 1982).
Confirmed Objective response, DOR, DRR, and PFS according to RECIST 1.1 assessed by Investigator	Definition and analyses to be performed on the efficacy endpoints as assessed by Investigator will be similar to the endpoints as assessed by the Investigator, see above.
CI= confidence interval, CR=complete response, DOR=duration of response, DRR=durable response rate, IRC=Independent Review Committee, ORR=objective response rate, OS=overall survival, PD=progressive disease, PFS= progression-free survival, PR=partial response, RECIST 1.1=Response Evaluation Criteria in Solid Tumors Version 1.1.	

9.4.2 Safety Analyses

All safety analyses will be performed on the Safety Analysis population (SAF).

The on-treatment period is defined as the time from the first study intervention administration to the last study intervention administration date + 30 days or the earliest date of subsequent anticancer drug therapy minus 1 day, whichever occurs first, unless otherwise stated.

Data collected after reinitiation of treatment will be summarized according to the specifications in the IAP.

Safety endpoints include AEs, AESIs, clinical laboratory assessments, vital signs, physical examination, and ECOG PS as described in Section 8.2.

The definitions, procedures for recording, evaluating, follow-up, and reporting of AEs are described in [Appendix 4](#).

TEAEs are those events with onset dates occurring during the on-treatment period or if the worsening of an event is during the on-treatment period. The incidence of TEAEs, regardless of attribution, and TEAEs defined as possibly related to bintrafusp alfa will be summarized by MedDRA preferred term and system organ class and described in terms of intensity and relationship to bintrafusp alfa. Any AEs with an onset or worsening date after the on-treatment period will be reported separately.

See Table 12 for safety endpoints and statistical analysis methods. The specifics for safety analysis will be defined in the IAP and finalized before database lock.

Table 12 Safety Endpoints and Statistical Analysis Methods

Endpoint	Statistical Analysis Methods
Primary	Not applicable
Secondary Occurrence of TEAEs and treatment-related AEs	
The safety endpoints will be tabulated using descriptive statistics.
 
Participants will be analyzed according to the actual treatment they receive.The safety endpoints will be analyzed using descriptive statistics.The incidence of TEAEs, SAEs, treatment-related AEs, AESIs, and irAEs will be summarized by preferred term and system organ class for each treatment arm, and described in terms of severity and relationship to treatment.The worst on-treatment grades for chemistry and hematology laboratory results will be summarized.Shifts in toxicity grading from Baseline to highest grade during the on-treatment period will be displayed.For laboratory tests without an NCI-CTCAE grade definition results will be presented categorically (e.g., below, within, or above normal limits). 
Further details of safety analyses (including AEs, clinical laboratory assessments, vital signs, physical examination, ECG parameters, and ECOG PS) will be provided in the IAP.

AE=adverse event, AESI=adverse event of special interest, ECG=electrocardiogram, ECOG PS=Eastern Cooperative Oncology Group performance status, IAP=Integrated Analysis Plan, irAE=immune-related adverse event, NCI-CTCAE=National Cancer Institute Common Terminology Criteria for Adverse Events, SAE=serious adverse event, TEAE=treatment-emergent adverse event.

9.4.3 Other Analyses

Analysis of efficacy variables may be performed on subgroups of interest as needed. The detailed subgroups will be outlined in the IAP.

Serum concentrations of bintrafusp alfa will be determined by a validated method at the times listed in the Bintrafusp alfa Pharmacokinetic, Immunogenicity Sampling ([Table 2](#)). Samples for ADA assessments will be collected per the Schedule of Activities. The immunogenicity testing strategy is in accordance with current regulatory guidance documents and industry best practices.

PK, immunogenicity and biomarker [CCI](#) will be specified in the IAP finalized before database lock. The PopPK analysis and exposure-response may be performed using

combined data from several bintrafusp alfa clinical studies and will be specified in a separate IAP. Integrated analyses across studies, such as the PopPK analysis, exposure-response and biomarker analyses will be presented separately from the main CSR.

9.4.4 Sequence of Analyses

The planned efficacy analyses are specified below. Details of all planned analyses will be defined in the IAP:

- The interim analysis on unconfirmed response as assessed by the Investigator will be performed 4 months after the accrual of the first 15 participants.
- The primary analysis on objective response as assessed by an IRC will be performed 8 months after the accrual of the last participant. At the same time, the analysis of durable response of at least 6 months assessed by an IRC will be performed to support the ORR data. The analysis of DOR and PFS will be performed as well to support efficacy assessment of bintrafusp alfa.
- A final analysis will be performed for evaluation of OS 24 months after accrual of last participant.
- If the study continues after the cutoff date for final analysis, subsequent analyses may be performed.

10

References

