- In the case of PD, treatment may continue past the initial determination of PD or confirmed PD if the participant's performance status has remained at least stable, and if in the opinion of the Investigator, the participant will benefit from continued treatment and if other criteria are fulfilled as outlined in the protocol.
- In the case of stable disease, partial response, or complete response, treatment should be continued until the end of 24 months. If the Investigator believes that a participant will benefit from treatment beyond 24 months, it may be permissible after discussion with the Medical Monitor and the Sponsor Medical Responsible.
- Safety Follow-up will continue until 12 weeks after the last dose of bintrafusp alfa. The 12-week Safety Follow-up is allowed to be conducted via telephone calls or patient chart reviews unless there is medical necessity requiring a clinical visit.
- Long-term Follow-up for progression and survival should be performed every 12 weeks after the Safety Follow-up according to the Schedule of Activities. Long-term Follow-up should be performed by patient chart reviews or telephone calls unless a clinical visit is indicated.

Number of Participants:

The planned total sample size is 29 female participants to address the primary and other efficacy objectives, safety assessments, and evaluation of the clinical utility of the RT-PCR-based assay for HMGA2. CCI

Assuming a true objective response rate of 30%, the probability to observe a lower bound of the exact 95% confidence interval above 10% (the benchmark for clinically non-relevant effect) would be 81% when analyzing 29 participants.

Study Intervention Groups and Duration:

[figure not shown]
The planned maximum study duration for a participant is estimated to be up to 24 months (in certain instances, this duration may be lengthened if it is in the best interest of the participant to continue further treatment). This includes a 28-day Screening period (decision will be made in this period for participants' study inclusion if all eligibility criteria are met); a treatment duration until confirmed PD, unacceptable toxicity, study withdrawal or death occurs, a 28-day Safety Follow-up Visit, a 12-week Safety Follow-up phone call after the last dose of bintrafusp alfa, and a Long-term Follow-up (performed every 12 weeks after the Safety Follow-up).

Involvement of Special Committee(s): Yes

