6.2 Primary Analysis

This analysis will be the main analysis and all planned analyses identified in the Clinical Study Protocol and in this IAP will be performed. All data will be included up to a clinical cut-off date corresponding to 8 months after the accrual of the last participant.

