6.3 Final Analysis

An extract of the primary analyses as specified in the TLF table of content will be done in the final follow-up analysis for evaluation of OS. All data will be included up to a clinical cut-off date corresponding to 24 months after accrual of last participant.

7 Changes to the Planned Analyses in the Clinical Study Protocol

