14.4 Secondary Endpoint: Progression-Free Survival as Adjudicated by IRC

Progression-Free Survival (PFS) time in months, is defined as the time from first administration of study treatment until the first documentation of progression of disease (PD) or death due to any cause, whichever occur first. The tumor response will be determined according to RECIST 1.1 and assessed by the IRC. PFS time will be calculated as follows:

$$PFS \text{ (months)} = \frac{(date \text{ of } PD \text{ or death or censoring} - date \text{ of first dose of study treatment} + 1)}{30.4375}$$

Tumor assessments will be measured at screening and during the intervention period: at week 9 day 57, week 17 day 113, then every 8 weeks (or until disease progression) for 12 months and then every 12 weeks or until disease progression (see Table 1 in the study protocol).

The following censoring rules will also be applied for the PFS computation:

- Participants with no event (PD or death) will be censored on the date of the last adequate tumor assessment
- Participants who do not have a baseline tumor assessment or who do not have any evaluable post-baseline tumor assessments will be censored at the date of first administration of study treatment unless death occurred on or before the time of the second planned tumor assessment (i.e. 17 weeks) in which case the death will be considered an event.
- Participants who start new anticancer treatment prior to an event will be censored on the date of the last evaluable tumor assessment before anticancer therapy is given.

Note: any systemic anticancer therapy, any anticancer surgery and any anticancer radiotherapy will be considered as new/subsequent anticancer therapy and will lead to censoring.

- Participants with an event after two or more subsequent missing response assessments (i.e. no assessments in 113 days prior to the event during the first 12 months [i.e. 365 days of follow-up] or 168 days prior to the event after the first 12 months of follow-up) will be censored on the date of the last evaluable tumor assessment.

The last tumor assessment date is defined as the last available and evaluable tumor assessment performed prior to the cut-off date (or prior to end of study, i.e. participants lost to follow-up or who withdraw consent) or prior to subsequent anticancer therapy.

Censoring rules are summarized in [Table 8](#) and [Table 9](#).

Table 8 Date of Event/Censoring Definition for PFS Analysis

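### Durable response is analysed 8 months after last accrual, too early on the 8-weekly scan schedule for late-enrolled ongoing responders to show 6 months, so the planned DRR is biased down

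*Protocol*

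**What the plan says.** - **Timing.** Protocol 9.4.4 sets the primary analysis 8 months after last accrual and adds that on that occasion "the analysis of durable response of at least 6 months assessed by an IRC will be performed to support the ORR data". SAP 6.2 agrees: "All data will be included up to a clinical cut-off date corresponding to 8 months after the accrual of the last participant". SAP 9.1 keeps later data out of every analysis.
- **Scans.** SAP 14.4 places them "at week 9 day 57, week 17 day 113, then every 8 weeks" up to 12 months, then 12-weekly. Protocol Table 1 gives W49 as the 12-month example and allows 7 days either side of each scan.
- **DOR.** Under Protocol Table 11 and SAP 14.6 it runs from the first CR/PR scan of a confirmed response to progression or death, with the PFS censoring rules. A participant without an event is censored at the last adequate tumor assessment.
- **Durable response.** Protocol Table 11 has censored participants "treated as failures (successes) in the analysis of durable response if the censored DOR is before (at least) 6 months". SAP 14.6 differs: any censored DOR counts as not reaching 6 months. Its denominator is all participants.
- **24 months.** Protocol 9.4.4 describes the final analysis for OS. SAP 6.3 says an extract of the primary analyses, to be listed in the TLF table of contents, "will be done in the final follow-up analysis for evaluation of OS".
- **Status.** SAP 4.1 records the early discontinuation and states that efficacy will not be analysed.

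**The concern.** Eight months looks sufficient at first sight: about 2 months to the first scan plus 6 months of response. A response first seen on Day 57 would pass 6 months on about Day 239, just inside the cut-off. But an ongoing response is credited only up to its last scan, and the next scan after Day 225 falls well beyond the cut-off. Late-enrolled responders who are still responding are then scored as failures while remaining in the denominator.

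DRR is named among the key secondary objectives in Protocol 4.1 and is placed at this cut-off to support the ORR. A value lowered by the calendar and not by the drug would support it badly. Protocol 4.2 also foresees further cohorts or an extension towards registration, for which durability would matter.

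**Working it through.** **1. The plan's own figure.** With n = 29 (Protocol 1.1), the aim is a "lower bound of the exact 95% confidence interval above 10" per cent when the true ORR is 30%. The Clopper-Pearson lower bound is 8.0% for 6/29 and 10.3% for 7/29, so 7 responders are needed. P(X ≥ 7 | n = 29, p = 0.30) = 0.812, which reproduces "would be 81% when analyzing 29 participants". This figure concerns ORR only. A response first seen at scan 1, 2 or 3 can be confirmed at the next scan, Day 225 at the latest, so the cut-off does not disturb it.

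**2. Cut-off.** SAP 9.5 takes a month as 30.4375 days: 8 × 30.4375 = 243.5 days, about Day 244 for the last participant if first dose falls on the accrual date. Any gap between accrual and first dose makes matters worse.

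**3. Nominal scan days.** 57, 113, 169, 225, 281, 337 (W49), then 337 + 84 = 421.

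**4. DOR for an ongoing response.** DOR in months = (last scan − first response scan + 1)/30.4375 (SAP 14.6). Six months is 182.6 days.

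| First response | DOR at Day 225 | First scan giving ≥ 6 months | DOR there | Months after first dose | Beyond 8 months |
|---|---|---|---|---|---|
| Day 57 | 169/30.4375 = 5.55 | Day 281 | 225/30.4375 = 7.39 | 280/30.4375 = 9.20 | 1.20 |
| Day 113 | 113/30.4375 = 3.71 | Day 337 | 225/30.4375 = 7.39 | 336/30.4375 = 11.04 | 3.04 |
| Day 169 | 57/30.4375 = 1.87 | Day 421 | 253/30.4375 = 8.31 | 420/30.4375 = 13.80 | 5.80 |

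**5. Scan windows.** With ±7 days on both scans, only a first scan on Day 50 with the fourth on Day 232 reaches 6 months: (232 − 50 + 1)/30.4375 = 6.01. That is 1 of 15 × 15 = 225 day combinations. A Day 57 responder who dies between Day 239 and the cut-off would also count as durable, whereas one still alive and responding would not.

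**6. Size (assumptions, since accrual length and response timing are not given).** Take uniform accrual over A months and first responses split 60/30/10% over scans 1 to 3. The share of truly durable responses not yet visible at the cut-off is (0.6 × 1.20 + 0.3 × 3.04 + 0.1 × 5.80)/A = 2.21/A.

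For the true DRR, a confirmed responder must stay progression-free for 112 days after the confirming scan (for example Day 113 to Day 225), because progression first seen at the following scan already gives more than 6 months. With a constant hazard and a 12-month median this has probability 2^(−112/365.25) = 0.81. DRR = 0.30 × 0.81 = 24.3%, or about 7.0 of 29.

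| A (months) | Share missed, 2.21/A | Participants missed (7.0 × share) | DRR seen at 8 months |
|---|---|---|---|
| 6 | 0.369 | 2.6 | 24.3 × 0.631 = 15.3% |
| 12 | 0.184 | 1.3 | 24.3 × 0.816 = 19.8% |
| 18 | 0.123 | 0.9 | 24.3 × 0.877 = 21.3% |

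Each participant is worth 1/29 = 3.4 percentage points. If the 12-month median is instead applied from first response straight to 6 months, DRR is 0.30 × 2^(−6/12) = 21.2%, or 6.15 of 29, and the loss is 6.15 × 0.369 = 2.3 down to 6.15 × 0.123 = 0.8 participants.

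All these figures use the Protocol Table 11 rule. Under SAP 14.6 every ongoing responder is a failure at any cut-off.

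**The case against.** - **Durability is already shown with censoring handled.** SAP 14.6 plans Kaplan-Meier DOR rates with intervals at 6 months and other times, swimmer graphs, and a listing that shows whether each response is ongoing. Protocol 9.4.4 runs DOR at the same cut-off. This stands and softens the consequence, but it does not correct the reported DRR.
- **The 24-month analysis may repeat DRR.** A reader might infer that it is confined to OS. The documents do not support that: SAP 6.3 refers to an extract specified in the TLF table of contents, which is not available here. What can be said is that neither document states that DRR is repeated.
- **The size is driven by assumptions and may be small.** A reader might take the 37% share at 6 months' accrual as the expected loss. Protocol 2.2 projects that about 12% of TNBC patients have high HMGA2 expression, so accrual that fast may be optimistic. At 12 to 18 months the shift is 4.5 to 3.0 points, small beside an exact 95% interval of 10.3% to 43.5% for 7/29. This stands, but the bias always runs in one direction and no accrual length removes it.
- **The bias is conservative.** No decision rule for DRR is visible in the text, and a downward bias in a single-arm trial cannot create false efficacy. That is fair, and it limits the weight of the point.
- **No efficacy analysis will be run.** SAP 4.1 settles this. A reader should not infer that any reported result of this study is affected.

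**Conclusion.** The point holds for the design as planned before the early discontinuation. With the cut-off at 8 months, DOR censored at the last adequate scan and a DOR censored before 6 months counted as a failure, a last-enrolled ongoing Day 57 responder stands at 5.55 months and fails. On nominal scan days the shortfall reaches participants first dosed in roughly the last 1.2, 3.0 and 5.8 months of accrual, for responses first seen at scans 1, 2 and 3. Under the stated assumptions (uniform accrual over 6 to 18 months, 60/30/10% split, ORR 30%, median DOR 12 months, Protocol Table 11 rule), about 2.6 to 0.9 of 29 participants are misclassified. The direction follows from the documents; the size does not, because accrual length is not stated.

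It would be wrong to conclude that a later cut-off alone repairs DRR: while SAP 14.6 counts every censored DOR as a failure, a responder still in response fails whenever the analysis is done. ORR and its 81% figure are unaffected, and so is this study's abbreviated report.

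**What to change.** 1. Align SAP 14.6 with Protocol Table 11, so that a DOR censored at 6 months or later counts as durable. This must come first, because the second step does not help ongoing responders without it.
2. State in Protocol 9.4.4 and SAP 6.2 and 6.3 that the definitive DRR and DOR are analysed at the final analysis, 24 months after last accrual. Label the 8-month DRR preliminary and present it beside the Kaplan-Meier 6-month DOR rate already planned.

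Restricting the 8-month DRR to participants dosed at least 14 months before the cut-off is not a good substitute. It removes everyone from the last 6 months of accrual (14 − 8), which leaves essentially nobody if accrual takes 6 months.

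The cost is wording in both documents and one repeated table at an analysis already scheduled. Protocol 8.1 continues scans through Long-term Follow-up, so no added participants or scans are needed. The downside is that the definitive DRR arrives later than the ORR. Given SAP 4.1, the change matters only if the design is resumed, extended or reused.
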